### **11.2 BLINDING AND UNBLINDING**

Idronoxil will be administered at escalating doses in an open-label fashion. Patients will be allocated to 1 of 2 cohorts. No randomization or stratification is required.

## **12 DATA COLLECTION AND MANAGEMENT**

### **12.1 METHODS**

The Principal Investigator must ensure there will be primary source documentation for all patient data collected as part of the study, and the data will not be recorded directly onto the CRFs without the availability of such primary documentation, except for cases in which the Sponsor has predetermined that direct data entry into specified pages of the patient's CRF is appropriate. The source data may include such documents as clinical notes, laboratory result sheets, pathology reports, radiology results, etc., and will be retained in each patient's medical record or research chart. CRFs will be provided by the Sponsor.

The Principal Investigator will be responsible for the timeliness, completeness, and accuracy of the information entered on the CRF. The Principal Investigator will provide access to the Medical Monitor or designated Sponsor representative(s) for the periodic review of all study records, source documents among other records for review and inspection to assure accuracy and completeness of the CRFs. All CRFs will be 100% source verified against corresponding source documentation (e.g., office and clinical laboratory records) for each patient.

The Sponsor and designated Sponsor representative(s) will maintain frequent contact with each site to assure the study is conducted according to the protocol and that all data collected are accurate and complete. Any deficiencies identified during the study will be communicated to the site for prompt correction.

#### **12.1.1 Case Report Form**

All information relative to the study will be recorded into a 21 CFR part 11 FDA compliant electronic Case Report Form (eCRF). Data corrections will be entered by the authorised site personnel.

#### **12.1.2 Return and Storage of Forms**

The Investigator will retain the copies of the CRF and all other study related documents for 15 years from completion of the study in accordance with National regulations.

### **12.2 DATA MANAGEMENT**

#### **12.2.1 Data Coding**

Medications will be coded from the WHO Drug Dictionary and medical history and adverse events will be coded using the MedDRA terminology for System Organ Class (SOC) and Preferred Term (PT).

### **12.2.2 Data Validation**

A Data Management Plan which fulfils the requirements for ICH GCP will be developed to describe all manual and electronic validation checks of the data prior to analysis. Data queries requiring clarification will be documented on the EDC eCRF for the investigational site to resolve. Only authorised personnel will make corrections to the clinical database, and all corrections will be documented in an electronic audit trail

## 13 STATISTICAL SECTION

### 13.1 SAMPLE SIZE

This is a sighting study intended to determine the safety of idronoxil (as NOX66 suppository dosage formulation) in combination with carboplatin, and to provide guidance as to the dosage combination of the two drugs that will be taken into later studies. A minimum of 8 patients per combination is considered adequate.

### 13.2 STATISTICAL METHODOLOGY

This section describes the planned statistical analyses in general terms. A complete description of the statistical analysis will be specified in a statistical Analysis Plan (SAP) finalised prior to completion of the study.

The primary objectives of this study are to determine

- (a) the tolerability, adverse event profile and any dose limiting toxicities (DLTs) of idronoxil (as NOX66) in combination with carboplatin in patients with refractory solid tumors, and
- (b) the ability of idronoxil (as NOX66) in combination with carboplatin to deliver a meaningful anti-cancer effect in refractory tumours considered unlikely to respond to carboplatin.

Secondary objectives are:

- 1) to characterize the pharmacokinetic profile of idronoxil administered rectally as NOX66, and
- 2) to determine any correlation between biomarkers of idronoxil biological activity and any clinical anti-tumor activity or toxicity observed in patients treated with NOX66.

These objectives are to be addressed in the context of an open-label, dose-escalation study; therefore, statistical hypothesis-testing will not be performed, and analyses will be primarily descriptive in nature.

All patients will be included in the safety evaluation. Data will be presented by dose cohort. Data from Study NOX66-001A will be used to guide dosing for future Phase II trials.

**Populations for Analysis:** There will be three study populations defined for this study.

The safety population will consist of all patients who received at least one dose of idronoxil. This population will be used in all safety summaries.

The efficacy population will consist of all patients with measurable or evaluable disease at baseline who complete at least 1 cycle of treatment and undergo at least one follow-up tumor

evaluation.

The pharmacokinetic/biomarker population will be a subset of the safety and efficacy populations and consist of all patients who have sufficient idronoxil plasma data for analysis. All such patients will be evaluated unless significant protocol deviations have impacted the data. Changes to the procedures, which may impact the quality of pharmacokinetic data, will be considered significant protocol deviations. Examples include sample processing errors that lead to inaccurate bio- analytical results and/or inaccurate dosing on the day of pharmacokinetic sampling.

**General Methodology:** In general, data will be summarized by using counts and percents for discrete parameters, and by descriptive statistics (number of observations, mean, standard deviation, median, minimum and maximum) for continuous parameters. Subject disposition and baseline characteristics will be presented by dose cohort for all treated patients. Data will be analysed as collected. No imputation of missing data is planned. All collected data will be presented in the data listings by dose cohort.

**Baseline Comparisons and Patient Disposition:** Demographic and baseline disease characteristic data summarization will be performed in order to descriptively assess the comparability of dose cohorts. Data to be tabulated will include demographic features such as gender, age, and race, as well as disease specific status and medical history. The number and percentage of patients who complete the study or who withdraw for any reason will be presented by dose cohort.

**Safety Analysis:** The safety will be assessed through the analysis of the reported incidence of treatment emergent AEs, including SAEs, dose-limiting toxicities, AEs leading to withdrawal, events of at least CTCAE Version 4.03 Grade 3 in severity, and AEs related to study treatment. Treatment emergent AEs are those with an onset on or after the initiation of therapy. Other safety endpoints include laboratory results, ECG findings, physical examinations, vital signs, and changes in ECOG status. A copy of CTCAE Version 4.03 scoring system may be downloaded from: [http://evs.nci.nih.gov/ftp1/CTCAE/CTCAE\\_4.03\\_2010-06-14\\_QuickReference\\_8.5x11.pdf](http://evs.nci.nih.gov/ftp1/CTCAE/CTCAE_4.03_2010-06-14_QuickReference_8.5x11.pdf).

The adverse events will be summarized by MedDRA coding terms, System Organ Class (SOC), and preferred term for all treated patients and by dose cohort. The AEs will also be tabulated by maximum severity and maximum relationship to study drug where applicable. The number and percent of patients experiencing dose-limiting toxicities will be summarized by dose cohort, by DLT, and system organ class for all treated patients. Other safety endpoints, which include change from baseline in laboratory results and vital signs, and shifts in ECG findings and physical examinations, will be summarized throughout the study by visit for each dose level for all treated patients.

ECG parameters at each time point will be presented by patient and by time point. The results will be presented by dose cohort.

**Efficacy Analysis:** Tumor measurements will be assessed by radiologic methods at baseline and at subsequent intervals at the discretion of the Investigator but not greater than every 12 weeks. Efficacy variables will include overall response, duration of objective response, time to progression, progression free survival (PFS), and overall survival. Response and progression will be assessed according to RECIST (Eisenhauer et al., 2009).

Continuous data will be summarized by descriptive statistics, including sample size, mean, standard deviation, median and range. Categorical data will be summarized by the number and percentage of patients. For the time-to-event endpoints, Kaplan-Meier estimates will be plotted.

Median event time and the associated 95% confidence interval will be provided. In addition, all the data will be presented in the data listings. The final statistical analysis for the study will be scheduled when all patients have completed at least one course of study drug administration, have reached a study endpoint (e.g., DLT or disease progression), and have at least 28 days of follow-up.

Best overall response, duration of objective response (complete response or partial response), PFS, time to progression and overall survival will be listed for all patients with measurable or evaluable disease by dose level. Any patient with insufficient data to determine response will be classified as a non-responder. Among patients with an objective response, duration of objective response will be defined as the time from the initial CR or PR to the time of disease progression or death on study, whichever occurs first. For patients who are alive and have not experienced disease progression on study, duration of objective response will be censored at the day of the last tumor assessment. Time to disease progression is defined as the time from the first day of study drug administration (Day 1) to disease recurrence or progression on study. Progression free survival (PFS) is defined as the time from the first day of study drug administration (Day 1) to disease recurrence or progression, or death on study. Patients who are alive and disease progression-free will be censored at the date of last disease evaluation.

**Pharmacokinetics:** Plasma and 24-hour urine levels of idronoxil and idronoxil metabolites (idronoxil glucuronide, idronoxil sulphate) will be measured. Pharmacokinetic parameters will minimally include  $C_{max}$ ,  $T_{max}$ ,  $AUC_{0-24hr}$ ,  $AUC_{0-\infty}$ , and  $t_{1/2}$  and be calculated using standard analysis. Descriptive results will be presented for the pharmacokinetic parameters by dose cohort.

In the event that PK concentrations are not detectable at the time points necessary and a meaningful PK curve (i.e. concentration vs time) cannot be estimated, descriptive statistics will be used to summarize PK concentration.

**Concomitant medications:** Concomitant medications will be listed by dose cohort for all patients.

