#### **8.5 PATIENT REPLACEMENT**

Patients who cannot be evaluated as part of the efficacy analysis may be replaced in the study up to total of 16 evaluable patients.

Replacement will occur at end of all safety cohort assessments and patient may be enrolled at the highest tolerated dose level, commencing with treatment cycle 1 of Phase 1b.

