**Table 2. NOX66/Idronoxil Dose Level Schema**

Treatment Regimen/ Cohort	NOX66 Dosage	Daily Idronoxil Dosage
1	One suppository, once daily	400 mg
2	One suppository, twice daily (12-hourly)	800 mg

Patients remain on the same daily dosage of idronoxil throughout all arms of the Study.

Idronoxil will be administered over a 21-day Treatment Cycle comprising daily NOX66 administration for 14 consecutive days followed by 7 days of rest.

Once Cohort 1 has enrolled 4 patients, further recruitment to that cohort will be suspended until the fourth evaluable patient completes 1 Treatment Cycle (including the 7-day rest period) and at least 3 of the 4 patients have not experienced any toxicity > Grade 2. The remaining 4 patients in Cohort 1 may then be recruited and start treatment.

Cohort 2 patients may commence idronoxil treatment once all 8 Cohort 1 patients have completed 1 (21-day) Treatment Cycle and at least 6 of those patients have not experienced any toxicity > Grade 2.

Where MTD is deemed to have been reached, up to 6 additional patients may be recruited into the particular cohort in order to confirm the tolerability of the MTD. However, it is not expected that MTD will be reached in this study.

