#### **10.1.4 Definition and Determination of Dose Limiting Toxicity (DLT) and Maximum Tolerated Dose (MTD).**

The Maximum Tolerated Dose (MTD) of idronoxil as a monotherapy in the Phase Ia Run-In Arm will be defined as the dose level immediately below the dose level at which 2 of the first 4 patients per cohort (or at least 3 of 8 patients) during the first cycle of that particular Treatment Regimen experience DLT (related to therapy). Additional patients will be recruited so that at least 6 patients are treated at the designated MTD, with no more than 1 DLT observed among the 6 patients. The MTD will be defined in terms of NCI-CTC graded toxicity during the patients' treatment cycle (21 days).

A dose limiting toxicity (DLT) will be defined as any one of the following occurring during the first treatment cycle 1:

- NCI-CTCAE  $\geq$  Grade 3 neutropenia lasting  $\geq$  5 days OR febrile neutropenia (fever  $\geq$  38.5°C) Grade 4 thrombocytopenia, or Grade 3 thrombocytopenia associated with bleeding;
- NCI-CTCAE  $\geq$  Grade 3 abnormal laboratory values (except neutropenia and thrombocytopenia) that are assessed as clinically significant and causally associated with NOX66;
- NCI-CTCAE  $\geq$  Grade 3 non-laboratory toxicity that is assessed as causally associated with NOX66; (excluding alopecia, rash, nausea, diarrhea, and vomiting if controlled with standard supportive therapy);

Once any DLT is reported, at least two more patients will be enrolled at the same dose level. Escalation will continue only if a DLT is limited to one of 4 patients. If a DLT occurs in 2 or more patients, further dose escalation will cease and the MTD will be the next lower level.

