3.1 Analysis populations

There will be three study populations defined for this study.

The safety population will consist of all patients who received at least one dose of NOX66. This population will be used in all safety summaries.

The efficacy population will consist of all patients with measurable or evaluable disease at baseline who complete at least 1 cycle of combination treatment and undergo at least one follow-up tumour evaluation.

The pharmacokinetic/biomarker population will be a subset of the safety and efficacy populations and consist of all patients who have sufficient NOX66 plasma data or biomarker plasma data for analysis. All such patients will be evaluated unless significant protocol deviations have impacted the data. Changes to the procedures, which may impact the quality of pharmacokinetic data, will be considered significant protocol deviations. Examples include sample processing errors that lead to inaccurate bio-analytical results and/or inaccurate dosing on the day of pharmacokinetic sampling.

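### The planned DLT percentage has no DLT-evaluable denominator and no split by phase, so it does not estimate the run-in DLT rate

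*Protocol*

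**What the plan says.** Protocol 13.2 gives the only rule for the DLT summary: the number and "percent of patients experiencing dose-limiting toxicities will be summarized by dose cohort, by DLT, and system organ class for all treated patients". The same section defines the set behind all safety summaries: "The safety population will consist of all patients who received at least one dose of idronoxil". No minimum exposure or follow-up is required. The SAP keeps to this structure (3.1): "There will be three study populations defined for this study". They are safety, efficacy and pharmacokinetic/biomarker; none is a DLT-evaluable set.

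The endpoint is tied to a window. Protocol 10.1.4 states: "A dose limiting toxicity (DLT) will be defined as any one of the following occurring during the first treatment cycle 1". For the monotherapy MTD it adds: "The MTD will be defined in terms of NCI-CTC graded toxicity during the patients' treatment cycle (21 days". The enrolment hold in protocol 10.1.1 also depends on a completed window: "further recruitment to that cohort will be suspended until the fourth evaluable patient completes 1 Treatment Cycle (including the 7-day rest period". What makes a patient evaluable for this purpose is not defined.

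Protocol 8.5 allows replacement of patients who cannot be evaluated for efficacy, and says of a replacement that the "patient may be enrolled at the highest tolerated dose level, commencing with treatment cycle 1 of Phase 1b". SAP 3.3 places replacements in the combination phase of the highest tolerated dose cohort.

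DLTs are not confined to the run-in. Protocol 7.1 makes the step up in carboplatin after three cycles conditional on there being no DLT, and 10.1.2 describes DLTs in the Combination Arm. SAP 8.2 splits adverse events into Phase 1a, combination at AUC4 and combination at AUC6, but neither 8.2 nor the table list in SAP section 11 contains a DLT table.

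**The concern.** The first primary objective (protocol 6.1) asks for DLTs and the MTD of NOX66 both alone and with carboplatin. One percentage per dose cohort, over everyone who took a dose, does not clearly answer either half.

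Two groups do not belong in the denominator of a run-in rate. Patients who stop before the 21-day window closes without a DLT are counted as having had none, although their window was not fully observed. Replacements who enter at Phase Ib had no monotherapy window, and any first-cycle DLT they have occurs on the combination.

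Replacement may also be linked to the event being measured. A DLT is a withdrawal criterion in 8.4, and 9.4 withdraws run-in patients with related Grade 3 or higher events, whereas the synopsis and 10.1.1 describe a dose reduction; these passages must be reconciled. A patient withdrawn in the run-in does not complete the combination cycle that SAP 3.1 requires for efficacy. That patient may therefore be replaced by someone who never enters the run-in.

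The stake is the interpretation of a reported primary-objective result. Protocol 13.2 says the study data will guide dosing in later Phase II trials.

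**Working it through.** The documents state no DLT rate, target rate, confidence level for a DLT rate, or expected dropout, so there is no planned figure to reproduce.

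**Inputs from the documents**
- Patients per cohort: 8 (protocol 7, 10.1.1).
- Planned Phase I total: 2 × 8 = 16 evaluable; maximum 22 (synopsis). Room above 16: 22 − 16 = 6.
- Run-in window: 21 days (10.1.4).
- Replacements: enter at Phase Ib cycle 1 (8.5), highest tolerated dose cohort only (8.5, SAP 3.3).

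**Assumed, because the documents give no figures**
- x = patients with a run-in DLT.
- c = further patients whose DLT occurs in the combination phase.
- e = patients leaving the run-in before Day 21 without a DLT (0 to 2).
- r = patients entering the cohort at Phase Ib (0 to 6).

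**Formulas**
- Run-in rate among patients with a DLT or a completed window: x / (8 − e).
- Planned percentage, run-in DLTs only: x / (8 + r).
- Planned percentage, both phases counted: (x + c) / (8 + r).

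| x | c | e | r | Run-in evaluable rate | Planned all-treated percentage |
|---|---|---|---|---|---|
| 2 | 0 | 0 | 0 | 2/8 = 25.0% | 2/8 = 25.0% |
| 1 | 0 | 1 | 0 | 1/7 = 14.3% | 1/8 = 12.5% |
| 1 | 0 | 0 | 1 | 1/8 = 12.5% | 1/9 = 11.1% |
| 1 | 0 | 1 | 1 | 1/7 = 14.3% | 1/9 = 11.1% |
| 2 | 0 | 2 | 2 | 2/6 = 33.3% | 2/10 = 20.0% |
| 1 | 0 | 0 | 6 | 1/8 = 12.5% | 1/14 = 7.1% |
| 1 | 1 | 1 | 1 | 1/7 = 14.3% | 2/9 = 22.2% |
| 1 | 1 | 1 | 6 | 1/7 = 14.3% | 2/14 = 14.3% |

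**Reading the table**
- With no early leavers and no direct entrants, and only run-in DLTs counted, the two figures agree. With no DLTs, both are 0%.
- With only run-in DLTs counted and at least one of them, every early leaver or direct entrant opens a gap, always downward.
- Once combination DLTs enter the numerator, the direction is not fixed: the planned figure is above the run-in rate in the seventh row and equals it by coincidence in the eighth.
- The 1/14 row puts all six places above 16 into one cohort as direct entrants. It is an upper bound on dilution within the cap, not an expectation.

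Phase IIa patients are left out because the documents do not say whether they would be pooled into the 400 mg and 800 mg columns.

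**The case against.** A reader might infer that the plan understates the run-in DLT rate. The documents do not support that as a general statement. Protocol 13.2 does not promise a run-in rate; its DLT summary has no phase limit, and its restatement of the primary objective refers to the combination. A downward error needs a numerator limited to the run-in, at least one run-in DLT, and at least one early leaver or direct entrant in that cohort. This objection stands in full.

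A reader might also take the 1/14 figure as typical. Six replacements would require six patients not evaluable for efficacy, and 8.5 only permits replacement. Protocol 10.1.1 also gives another use for up to six extra patients, namely to confirm tolerability at the MTD. This stands too, and the dilution by replacements touches one cohort only.

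Third, no escalation or MTD decision uses the percentage. The rules work on counts, such as "2 of the first 4 patients per cohort (or at least 3 of 8 patients" in 10.1.4. Without replacements, the all-treated base of 8 even matches those counts better than a base of 6 or 7 would. This also stands, and it confines the issue to reporting.

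Fourth, SAP 3.3 analyses by study arm and cohort, SAP 4.1 and 4.2 report cycles completed and withdrawals by phase, and SAP 8.2 splits adverse events by phase. A reader could partly rebuild the right denominator. That softens the problem but does not change the stated DLT rule, and the SAP has no DLT table to which its phase split could apply.

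Finally, 14.3% against 12.5% for one early exit is small beside the imprecision at n = 8: the exact 95% interval for 1/7 runs from 0.4% to 57.9%. True, but imprecision does not make an undefined denominator acceptable for a primary objective.

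**Conclusion.** The point holds as a matter of definition and reporting. The DLT percentage in protocol 13.2 has neither a DLT-evaluable denominator nor a restriction by phase, so it does not estimate the monotherapy DLT rate, and it does not isolate the combination rate either.

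The size depends on assumed numbers of early leavers, replacements and DLTs. With one or two of each and only run-in DLTs counted, 14.3% becomes 11.1% or 33.3% becomes 20.0%. With one combination DLT added in a different patient to the one-of-each case, the table shows 22.2% against a run-in rate of 14.3%. With no early leavers, no direct entrants and no combination DLTs, nothing changes.

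The documents support neither a fixed downward bias nor any effect on the count-based escalation and MTD rules. What is affected is the reported DLT rate for a primary objective and the guidance it gives for later dosing. The change should be made.

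**What to change.** In protocol 13.2, replace the single DLT percentage by two, each by dose cohort:

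1. **Monotherapy:** the denominator is run-in patients who had a DLT in the 21-day cycle or completed that cycle.
2. **Combination:** the denominator is patients who started the combination and had a DLT or completed the combination DLT window. That window must first be settled: 10.1.4 confines a DLT to the first treatment cycle, whereas 7.1 and 10.1.2 recognise DLTs in the Combination Arm without stating a window. These passages need to be reconciled by those responsible for the clinical rules.

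Show the number of non-evaluable patients beside each percentage. Define the DLT-evaluable sets in SAP 3.1, and add the DLT table to SAP 8.2 and to the list in SAP section 11. Keep all treated patients as the base for the other safety tables.

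The cost is wording, one extra denominator per phase and one table. No new data are needed. The reported DLT rate may be slightly less favourable.
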